## **Introduction**

Chronic Obstructive Pulmonary Disease (COPD) is the 4th leading cause of mortality in Canada, and accounts for significant morbidity in patients affected by the disease. COPD is now seen as a disease that is both preventable and treatable. In order to better facilitate treatment for these patients, a number of national and international consensus guidelines have been developed to help physicians in the diagnosis and chronic management of these patients.

The Canadian Thoracic Society published guidelines on the management of COPD in 2007 (updated in 2008) to help physicians optimize the care of patients with COPD. The guidelines were based on current evidence within the medical literature. Despite the availability of guidelines for COPD (as well as other specialties), implementation of guidelines into daily clinical practice, remains a challenge.

Patients who experience an Acute Exacerbation of COPD (AECOPD) have an increased risk of mortality. They represent an important subset of patients with COPD who need their management urgently optimized, to guideline standards, in order to improve their survival. These patients most often present to their local emergency departments (ED) for the acute episode. For patients who are admitted to hospital, an opportunity exists to re-evaluate their chronic management and therefore optimize their care. However, for patients who are not admitted to hospital, follow up care is often left to their primary care physician (PCP), if they have one. Information regarding how frequently this occurs, and what the outcomes of these follow up visits with their PCP is unknown. Although the national rate of patient follow up of patients by their PCP within the first month following an AECOPD is unknown, locally it is only 30%. This low rate of follow up represents a lost opportunity for reassessment of both the acute and chronic management of these patients, as well, represents a delay in optimizing their care to help improve their long term survival. One of the factors contributing to this low rate of follow-up, is poor or delayed communication between the ED and PCP.

It is our belief that improving the communication between the ED and the PCP regarding patients, who are discharged from the ED after being treated for their AECOPD, will improve the rates of patient follow up. Furthermore, if the communication highlights care gaps in the chronic management of COPD, this may result in an adjustment in management such that the patients' treatment will be more in keeping with current guideline recommendations.

## **Methods**

This study will be a 1 year randomized controlled trial to assess the impact of the “Lung Attack Alert” on rates of follow up by PCP of their patients following presentation to the ED for an AECOPD. The tool being assessed is labeled as the “Lung Attack Alert”(see **Appendix 1**). This is a novel information sheet that is intended for the PCP. The Lung Attack Alert summarizes the following points:

- a) that the PCP’s COPD patient has had a presentation to the ED for an AECOPD but did not require a prolonged hospital admission;
- b) a description of the discharge management from the ED will be provided;
- c) a recommendation to the PCP to follow up with the patient within 1-2 weeks after discharge from the ED;
- d) Care gaps identified in the patients chronic management of COPD based on the Canadian Thoracic Society 2007(updated 2008) guidelines will be highlighted for the PCP to address at the next outpatient follow up

Each Lung Attack Alert will be **individualized** to the patients care gap(s) identified during screening.

This study will enroll consecutive patients who present to the ED at the University of Alberta Hospital and the North East Community Center (both located in urban Edmonton), who present with an AECOPD, but who do not require admission to hospital.

ED physicians or the study coordinator will screen patients who present to the ED with an AECOPD, who have recovered from the acute event and are considered safe for discharge. All patients will receive usual care within the ED prior to screening and entry into the study. This may consist of the use of any or all of the following: oxygen, acute bronchodilators (+/- use of nebulizers or MDI), administration of oral/IV corticosteroids, intravenous fluids, non-invasive ventilation (NIV), oral or intravenous antibiotics as required.

Patients will be screened by either the ED physicians who will notify our study coordinator regarding the eligibility of a patient or directly by the study coordinator. Eligible patients (**Appendix 2**) will be provided with a patient information sheet (**Appendix 3**) outlining the rationale for the study. If the patient is agreeable to participate, a consent form will be signed and witnessed by either the ED physician or study coordinator (**Appendix 4**). To be enrolled into the study patients must satisfy all inclusion and exclusion criteria.

**Inclusion:**

Appropriately signed and dated informed consent has been obtained

ED patients presenting with an acute exacerbation of COPD requiring treatment in the ED;

Previous physician-diagnosis of COPD (e.g., emphysema, chronic bronchitis or COPD) either previously or within the ED;

Age >40 years of age;

Current or former smokers of more than 10 pack years (number of packs of cigarettes {or pipe and/or cigars} smoked per day X the number of years of smoking);

FEV1/FVC ratio < 0.7 for age, sex and height (either known or determined within the ED);

Patients can read and comprehend English language.

**Exclusion:**

Patients presenting for prescription renewal;

Patients who require hospitalization;

Patients who **do not** have a primary care physician or patients for whom a family physician cannot be found;

Patients who have already been enrolled in the study;

Patients with a ED physician-diagnosis of primary asthma, pneumonia, HIV/AIDS, immuno-compromise, or life expectancy of < 90 days.

Patients who, in the opinion of the investigator, should be excluded.

Using concealment of allocation, patients will be randomized using computerized random numbers tables to control and intervention groups. Randomization will be in a 1:1 distribution between the control and intervention group.

Upon enrollment into the study, basic information regarding the patient and their disease status will be collected. An ED chart review will be completed to document ED care. **We will complete the COPD Assessment Test (CAT), a**

**new questionnaire for people with COPD. It is designed to measure the impact of COPD on a person's life and is freely available on the internet ([www.catesonline.org](http://www.catesonline.org)). See Appendix 6 for the complete set of information to be collected.**

All patients enrolled in the study will be discharged home with a standardized protocol for the outpatient management of the AECOPD (**Appendix 5**). This will include a standardized length and dose of both oral corticosteroids (oral prednisone 50 mg once daily X 10 days) and antibiotics (oral Doxycycline 100 mg twice daily X 5 days or Levofloxacin 750 mg once daily X 5 days). The dosage and length of therapy is based on current standards and recommendations outlined in the CTS 2007 (updated 2008) consensus guidelines. The standardized medications will be provided for the patient at no cost to the patient themselves by the Central Research Pharmacy at the University of Alberta Hospital).

After normal working hours(see below), when research staff are not available, patients who are eligible and who have consented to enter the study but have been discharged from the ED, will be contacted by the study coordinator the next morning by phone. Randomization will take place at that time and the appropriate process will take place thereafter. Those patients who are discharged from the ED will receive the outpatient treatment package (by the consenting ED physician) used in the study (Appendix 5) for the medical management of their AECOPD. The outpatient medication package will be readily available in the ED, in a reserved area for the study. This is to ensure that there is no delay in their treatment, as well, that their acute management does not impact the effect of the Lung Attack Alert.

As per the above randomization process, patients will be randomized into either the **control** group or the **intervention** group using a web-based randomization process (Epidemiology Coordinating and Research {EPICORE} Centre, Edmonton, AB; <http://www.epicore.ualberta.ca>).

The **control** group will be discharged from the ED, with the standardized outpatient protocol (Appendix 5) and will be advised to follow up with their PCP. They will be provided with general information regarding COPD in the form of the "Breathworks" program pamphlets established by the Canadian Lung Association. These are readily available in print and online, and they are information guides for patients with COPD. The patients will then be contacted by a research staff member unaware of the allocation of treatment at day 30 and 90 post discharge from the ED to discuss the primary and secondary outcomes (**Appendix 7**).

The **intervention** group will also be advised to follow up with their PCP, along with the standardized outpatient protocol for their acute exacerbation (Appendix

5). They will be provided with general information regarding COPD in the form of the “Breathworks” program. The intervention group will have the Lung Attack Alert form completed by the research study staff. The form will highlight the information already discussed earlier. This will then be faxed to their primary care physician by the study coordinator. The patients will then be contacted by a research staff member unaware of the allocation of treatment at day 30 and 90 post discharge from the ED to discuss the primary and secondary outcomes (**Appendix 7**).

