**Recruitment plan:**

We have full-time research staff nurses at the UAH (coverage 16 hours/day; 08:00-24:00 M-F; 10:00-18:00 S&S) and at the NECHC (8 hours/ day; 10:00-18:00). We will increase our coverage if the numbers indicate the need to do so. We anticipate 5/month at the UAH and 4/month at the NECHC. Approximately one year of enrolment (February 2010-March 2011) should provide the numbers required for this study.

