**Principal analysis of the primary outcome measure:**

The final analysis will be performed on an "intention to treat" basis. Using this approach, patients will be included in the analysis according to the group to which they were randomized. Baseline characteristics in the two treatment arms will be compared using univariate descriptive statistics. The principal analysis of 30-day relapse will be done using an unadjusted  $\chi^2$  comparing the proportion of events in each treatment group. A logistic regression procedure will be employed to adjust raw relapse proportions using significant co-variates (such as patient use of inhaled steroids, current smoking status, etc) which may influence outcomes

We chose the proportion of PCP visits within 30 days as a primary outcome measure rather than survival time to relapse. We believe that it is more relevant to both patients and physicians to know if the enhanced intervention will stimulate a PCP visit rather than examining relapse (which may be affected by age, severity, type of treatment received, smoking status, etc). Therefore, unadjusted  $\chi^2$  followed by logistic regression procedures were chosen over log-rank tests followed by Cox proportional hazards modelling. Both alternative analytic approaches mentioned will still be performed and reported.

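### No blocking or stratification by site is stated and site is not a pre-specified analysis term, so a two-site trial of 110 may give up a little precision that is cheap to keep

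*Combined protocol and SAP*

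**What the plan says.** The method of allocation is given in two places in the Methods. The paragraph after the exclusion criteria states that "patients will be randomized using computerized random numbers tables to control and intervention groups", with concealment, and that "Randomization will be in a 1:1 distribution between the control and intervention group". A later paragraph refers back to that process and adds that it is carried out "using a web-based randomization process" run by a coordinating centre. Blocking, stratification and minimisation are not mentioned anywhere.

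The sites are the "University of Alberta Hospital and the North East Community Center (both located in urban Edmonton"). Under Recruitment plan, research cover at the university hospital is given as "coverage 16 hours/day; 08:00-24:00 M-F; 10:00-18:00 S&S", and cover "at the NECHC (8 hours/ day; 10:00-18:00"). The same section says "We anticipate 5/month at the UAH and 4/month at the NECHC".

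Under Principal analysis of the primary outcome measure, the plan reads "The principal analysis of 30-day relapse will be done using an unadjusted" chi-square. That sentence names relapse, but the next paragraph of the section takes PCP visits within 30 days as the primary outcome, and the Outcomes section gives 90 days. That conflict is a separate matter; here the test is taken to apply to the proportion with a PCP visit. A logistic regression follows, with covariates chosen by significance from an open-ended list. Inhaled steroid use and current smoking are given as examples; site is not named.

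**The concern.** Site is the obvious stratification factor. One ED is in a university hospital and the other in a community centre, and weekday research cover is 16 hours against 8. Patients who consent when no staff are present are telephoned and randomised the next morning, so the route into the trial probably varies by site. If PCP follow-up also varies by site, a chance difference in site mix between arms adds noise to the treatment comparison. The unadjusted chi-square does not remove that noise.

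Uneven arm sizes are a second, lesser matter. They widen the confidence interval slightly but do not move the difference in proportions.

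The practical stake is precision and credibility. The trial gets one allocation. If it turns out visibly uneven by site and site was never pre-specified, any adjustment will look post hoc. A central web system that could normally carry blocks and strata is already in place.

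**Working it through.** **Inputs.** From Sample Size Considerations: 30% against 60% with a PCP visit, alpha 0.05, power 0.80, 98 patients (49 per group), 110 after about 10% attrition. From Recruitment plan: 5 and 4 patients a month, so 110 × 5/9 ≈ 61 and 110 × 4/9 ≈ 49. Assumed: simple 1:1 allocation, and a site difference in PCP follow-up of 0, 10, 20 or 30 points, because the documents give none.

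**1. The plan's own figure.** With a mean proportion of 0.45, n per arm = [z_α √(2 × 0.45 × 0.55) + z_β √(0.3 × 0.7 + 0.6 × 0.4)]² / 0.3².
- Two-sided 0.05: [1.960 × 0.7036 + 0.842 × 0.6708]² / 0.09 = 42. With continuity correction, 49 per arm, or 98.
- One-sided 0.05: 33 per arm, or 40 with correction.

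So 98 is reproduced only as a two-sided calculation with continuity correction, not as the one-tailed calculation described. That is a separate point. Power below is two-sided 0.05. Attrition: 49 / 0.9 rounds up to 55 per arm, or 110.

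**2. Arm sizes under simple allocation.** With X ~ Binomial(110, 0.5):
- P(X ≤ 50 or X ≥ 60), a gap of 10 or more: 0.391.
- P(X ≤ 45 or X ≥ 65), a gap of 20 or more: 0.070.

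**3. What uneven arms cost.** Normal-approximation power for 30% against 60% is 89.6% at 55:55, 89.4% at 60:50 and 88.7% at 65:45. The 95% half-width of the difference is 1.96 × √(0.21/55 + 0.24/55) = 17.7 points at 55:55, at most 17.9 at 60:50 and at most 18.1 at 65:45.

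**4. Site mix under simple allocation.** The difference between arms in the share from one site has approximate SD √(0.555 × 0.445 × 2/55) = 9.5 points. Enumerating Binomial(61, 0.5) and Binomial(49, 0.5) gives 9.6. The difference exceeds 10 points with probability 0.288 and reaches 20 points or more with probability 0.037.

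**5. What that does to one trial's estimate.** The 95% limit for site mix is 1.96 × 9.57 = 18.75 points. Multiplied by an assumed site difference of 10, 20 or 30 points, it shifts the observed treatment difference by about 1.9, 3.7 or 5.6 points in either direction. These are 95% limits, not maxima. The target difference is 30 points.

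**6. Error rates.** Results of 100,000 simulated trials of 110 per scenario, two-sided 0.05 (CMH = Cochran-Mantel-Haenszel):

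| Assumed site difference | Type I error, simple + chi-square | Power, simple + chi-square | Power, simple + CMH | Power, stratified + CMH |
|---|---|---|---|---|
| 0 | 5.1% | 89.2% | 89.0% | 88.9% |
| 10 | 5.1% | 89.3% | 89.3% | 89.4% |
| 20 | 5.0% | 89.1% | 90.2% | 90.6% |
| 30 | 5.1% | 89.2% | 92.0% | 92.4% |

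The gain of the last column over simple allocation with chi-square is about 0 to 3 points. At 98 evaluable patients it is about 1 to 3.5 points, varying a little with the simulation set-up.

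Two things follow. Most of the gain comes from the site-stratified test rather than from the blocks. And stratified allocation followed by an unadjusted chi-square would be conservative: its type I error falls to 3.9% at a 30-point site difference. The analysis should therefore match the design.

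**The case against.** The strongest reply is that little is at stake, and most of that reply stands.

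- **Simple allocation is inferred.** Random-number tables can generate blocked lists, and the web system may already use blocks or strata. This stands. The probabilities in steps 2 and 4 depend on that reading, and what the text itself shows is an incompletely specified scheme.
- **The sites may not differ where it matters.** A reader might infer that PCP follow-up differs by site. The documents report no such difference. Both EDs are in one city, eligibility and the discharge package are common, every patient must have a PCP, and the intervention acts by fax at the PCP's office. This stands, and it is why a range that includes zero is shown.
- **Uneven arms do not bias the result.** A reader might infer that they shift the treatment difference or invalidate the chi-square. They do neither. The 39% and 7% figures sound large, but their consequence is the fraction of a point to about 1 point of power in step 3.
- **Chance site imbalance is already within the test's error.** This also stands: type I error is about 5% in every scenario.
- **Site is not excluded from the analysis.** The covariate list is open, so site could enter. This stands as far as it goes, but selection by significance is not pre-specified adjustment, and the principal test is unadjusted regardless.
- **Blocking is not free.** The coordinator may screen patients and faxes the alert for intervention patients only, so learns allocations, and exclusion at the investigator's discretion is allowed. With 4 or 5 patients a month per site, fixed small blocks could become guessable. Varying, undisclosed block sizes and central allocation limit this risk but do not abolish it.

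**Conclusion.** The point holds as a minor improvement in design and reporting. The plan does not state blocking or stratification, and it does not pre-specify site in the primary or adjusted analysis. If allocation is simple, sizeable chance imbalance in arm size and site mix is common. Its consequence is a modest loss of precision: about 0.2 points of power at 60:50, about 1 point at 65:45, and roughly 0 to 3.5 points to be gained from stratifying and testing by site.

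The upper end of that range requires an assumed site difference in follow-up as large as the whole 30-point target effect; at 10 points or less the gain is about 1 point at most. The documents do not support reading this as bias, an invalid test or a material loss of power. The conclusion rests on the simple-allocation reading, a 5:4 split by site and the assumed site differences.

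**What to change.** 1. **Methods, both randomisation paragraphs.** State how the sequence is generated. If it is not already so, set the web system to permuted blocks of varying size, stratified by site, with block sizes kept from site staff and held by the coordinating centre.
2. **Principal analysis of the primary outcome measure.** Replace the unadjusted chi-square with a Cochran-Mantel-Haenszel test stratified by site, and report the site-stratified risk difference with its confidence interval, for the PCP-visit outcome. Name site as a pre-specified term in the logistic and Cox models, not subject to selection by significance.

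The sample size stays at 110. The cost is a setting in a system already in use and a sentence or two of analysis text. The downside is slight predictability within site blocks, limited by varying concealed block sizes and central allocation. If the sequence can no longer be changed, the second step alone still recovers most of the gain.

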## **Outcomes**

The **Primary Endpoint** of this study is the rate of follow up of the patient by their primary care provider for review of the acute and chronic management of their COPD and addressing any issues on the Lung Attack Alert, within the first 90 days after discharge from the ED. The study coordinator will contact all patients enrolled on day 30 after admission to the ED to determine if a follow up visit has occurred and if any of the recommendations noted on the Lung Attack Alert have been implemented.

A number of **Secondary Endpoints** will be collected. These include 1) relapse of the AECOPD requiring acute intervention (ED or clinic) within the 90-day study period; 2) admission to the hospital within the 90-day study period; 3) review and adjustment of the management of COPD at day 90 post discharge from the ED 4) Proportion of patients who completed their acute management within the 90-day study period and 5) length of stay within the ED.

The study coordinator will contact the PCP of patients in the intervention group to survey the usefulness of the Lung Attack Alert once the study is complete. This survey will assess the clinical utility of the alert and the ease of use of the information provided in the alert to aid in clinical management.

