## **Statistics**

### **Sample Size Considerations:**

Calculations for the estimated sample size were completed using a formula for calculation of dichotomous response variables with two independent samples. We assumed  $\alpha = 0.05$  (accepted standard value), power  $(1 - \beta) = 0.80$ , and that 30% of patients in the control group would see their PCP within 30-days. This estimate of 30-day follow-up is taken directly from recent administrative data from Alberta. The sample size was therefore calculated to detect a 30% absolute difference in 30-day follow-up (30% of the standard-care vs. 60% of enhanced care groups). In addition, we used 1-tailed estimates due to the assumption that the intervention will not **decrease** the follow-up of patients with COPD. The total sample size was estimated at 98 (49/group) patients; however, if we assume ~10% attrition (see previous COPD study), the total sample size is estimated at 110 patients.

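### The primary outcome is defined at 90 days but sized and justified at 30 days, includes an element only the intervention arm can have, and its principal test is worded for relapse

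*Combined protocol and SAP*

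**What the plan says.** - **Outcomes.** The primary endpoint is the rate of PCP follow-up, for review of COPD management and "addressing any issues on the Lung Attack Alert", "within the first 90 days after discharge from the ED". The next sentence says the coordinator "will contact all patients enrolled on day 30 after admission to the ED" to find out whether a visit took place and whether Alert recommendations were acted on. Relapse within 90 days is the first secondary endpoint.
- **Methods, control and intervention groups.** Both arms are contacted at days 30 and 90 after ED discharge. On the Alert: "The intervention group will have the Lung Attack Alert form completed by the research study staff". Nothing equivalent is described for controls. Earlier in Methods, each Alert is tailored "to the patients care gap(s) identified during screening".
- **Sample Size Considerations.** The trial is sized on a "30% absolute difference in 30-day follow-up", 30% against 60%, with alpha 0.05 and power 0.80. The total is 98 (49 per group), raised to 110 for about 10% attrition. The section adds that "we used 1-tailed estimates due to the assumption that the intervention will not" reduce follow-up.
- **Principal analysis of the primary outcome measure.** "The principal analysis of 30-day relapse will be done using an unadjusted" chi-square test, followed by a logistic model for the relapse proportions. The next paragraph says the primary outcome is the proportion with a PCP visit within 30 days, explains why this was preferred to relapse, and ties the same two methods to that choice.

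**The concern.** Three features of one outcome disagree: the window (90 or 30 days), the variable in the principal test (PCP visit or relapse), and whether the definition can be applied to both arms.

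Both day-30 and day-90 data will exist, so each window will yield a result, and the document does not say which governs. A choice made after seeing results by arm would raise the type I error. The stated power applies to the 30-day visit alone. An outcome that requires acting on a form held for only one arm is not a like-for-like comparison. Read literally, controls either cannot meet it or must be scored by another rule.

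**Working it through.** **1. What the stated sample size belongs to.** Inputs from Sample Size Considerations: p1 = 0.30, p2 = 0.60 (both at 30 days), alpha 0.05, power 0.80. Allocation is 1:1 (Methods).

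Two-sided, uncorrected, with mean rate 0.45:

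n = [1.960·√(2·0.45·0.55) + 0.842·√(0.30·0.70 + 0.60·0.40)]² / 0.30² = 42 per arm.

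With continuity correction, n' = (n/4)·[1 + √(1 + 4/(n·0.30))]² = 49 per arm, total 98. This is the plan's figure. For attrition, 49/0.90 = 54.4, rounded up to 55 per arm, total 110, which also matches.

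The stated 1-tailed setting gives 33 per arm (total 66), or 40 (total 80) with correction. So 98 is the two-sided, corrected figure. That is a separate point. Here it matters only that 98 reproduces from the 30-day rates.

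**2. Power for the 30-day visit at 49 per arm.** Exact power sums the binomial probabilities of all outcome pairs for which the uncorrected chi-square rejects. For 30% vs 60% it is 86.6% two-sided and 91.1% one-sided. It exceeds 80% because the stated size carries the continuity correction. Fisher's exact test, two-sided, gives 81.5%.

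**3. Power if 90 days is primary.** The documents give no 90-day rate, so every rate below is an assumption.

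- *Equal visit hazards after day 30.* The share without a visit is 0.70 in controls and 0.40 in the intervention arm at day 30, and shrinks by the same factor in both. For control rate c, the intervention rate is 1 − 0.40·(1 − c)/0.70, and the gap is (1 − c)·3/7.
- *Effect persists at constant hazard.* Control 1 − 0.70³ = 65.7%; intervention 1 − 0.40³ = 93.6%.

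| Assumption after day 30 | Control, day 90 | Intervention, day 90 | Power, two-sided | Power, one-sided |
|---|---|---|---|---|
| Equal hazards | 35% | 62.9% | 80.9% | 86.2% |
| Equal hazards | 40% | 65.7% | 74.4% | 80.9% |
| Equal hazards | 50% | 71.4% | 59.0% | 70.8% |
| Equal hazards | 60% | 77.1% | 44.5% | 58.4% |
| Equal hazards | 65.7% | 80.4% | 37.6% | 50.3% |
| Effect persists | 65.7% | 93.6% | 95.8% | 97.8% |

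If the Alert only brings visits forward and the arms are equal by day 90, there is no 90-day difference to detect.

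**4. False-positive rate if either window may count.** Simulation of 400,000 trials at 49 per arm, no true difference, 30% visited by day 30 in both arms, rejecting if either two-sided test is significant at 5%. For common 90-day rates of 35%, 40%, 50%, 60% and 65.7%, the rates are 6.9%, 7.8%, 8.9%, 8.9% and 8.9%.

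**5. The two textual defects.** No arithmetic applies.

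- *Relapse.* The only sentence specifying the principal test names relapse, which Outcomes lists as secondary and for which no rate is assumed. The following paragraph argues for PCP visits instead. The wording is probably a carry-over, but taken literally it tests the wrong variable.
- *Alert element.* The form exists only for intervention patients, and no rule is given for scoring controls.

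**The case against.** The strongest reply is that the intent is clear. Both the sample size and the analysis rationale use a PCP visit within 30 days, and a statistician reading the whole analysis section is unlikely to test relapse as primary. The Alert phrase can be read as the purpose of the visit, not a second condition to be scored. The contact questionnaire (Appendix 7) is not in the supplied text and may settle this. The 90-day scenarios span so wide a range that they show no direction. Nothing in the plan proposes to claim success on either window, and choosing the window without sight of results by arm would cause no inflation. The day-30 contact being timed from ED admission is a minor slip, since Methods already times contacts from discharge.

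Much of this is fair. The relapse wording alone would be a minor correction, 90-day power is unknown and not shown to be low, and the inflation is conditional on a data-driven choice. But the formal endpoint definition still says 90 days, and a day-30 contact cannot determine a 90-day outcome. The purpose-of-visit reading is possible, but the text does not choose it, and the same section asks at day 30 about implementing Alert recommendations. A primary outcome that the reader must infer is not prespecified.

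**Conclusion.** The concern holds and must be fixed before outcome data are seen by arm. The window conflict is plain in the current text. The principal test names a secondary endpoint, and the definition contains an element that, as worded, cannot be scored in the same way for controls.

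The stated 98 patients support the 30-day PCP visit only. For the declared 90-day endpoint, two-sided power could lie anywhere from 38% to 96% in the scenarios tried, all of which rest on assumed 90-day rates. The 7% to 9% false-positive rate applies only if either window may be called primary after the results are known.

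**What to change.** Use one primary outcome throughout: a PCP follow-up visit within 30 days of ED discharge (yes/no), defined identically in both arms. It is the only window for which the plan gives a control rate, a sample size and a rationale.

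- **Outcomes.** Change the primary window to 30 days and list 90-day PCP follow-up as secondary. Take the Alert element out of the primary definition and report it separately. Time the day-30 contact from ED discharge, as Methods does.
- **Principal analysis of the primary outcome measure.** Replace relapse with 30-day PCP follow-up in both the chi-square and logistic sentences. Keep all relapse tests in the secondary section.
- **Optional.** If action on care gaps is to be compared between arms, score it against the gaps identified at screening, listed for every patient.

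The core change is wording only. All patients are already asked at day 30 whether a visit has occurred, no patients are added, and 98/110 stands. The optional comparison would require care gaps to be recorded for controls as well, a small extra data-collection task.
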